Intervention timeline. Each participant will complete a 2-arm (MFGM-Enriched Milk; Coconut/Palm Oil-Enriched Milk), randomized, cross-over study. For this study, each participant will visit the study center a total of 12 times (6 times per study arm, including 1) baseline measurements of anthropometrics, serum glucose, insulin, endotoxin, and pick-up of meals for days 1-3, 2) pick-up of meals for days 4-6, 3) pick-up of meals for days 7-10 and measurement of anthropometrics, 4) pick-up of meals for days 11-14 and stool collection kit, 5) 3 h postprandial testing, and 6) return samples from 24-h urine collection. Interventions will be separated by two weeks (for women, interventions will be separated by 2, 6, 10 etc. weeks to ensure testing will be performed at the same time of the menstrual cycle).

Baseline visit. On day 0 of each trial arm, participants will report in the fasted state (10-12 hours) to the study center for assessment of height, weight, waist circumference, blood pressure, serum glucose, serum insulin, and serum endotoxin. They will receive 3-4 days of meals plus MFGM-enriched milk or coconut/palm oil-enriched milk.

Dietary intervention. Participants will be provided all foods for the 14-d intervention period. After the baseline visit, participants will report back to the study center on days ~6 and 10 to pick up their meals for the proceeding 3-4 days. On day 7, anthropometrics (height, weight, and waist circumference) will also be measured to ensure weight maintenance.

Test trials. At the end of the intervention period (day 14), participants will report back to the laboratory in the fasted state (10-12 hours) for assessment of height, weight, waist circumference, blood pressure, plasma glucose, insulin, gastric inhibitory peptide (GIP), glucagon-like peptide-1 (GLP-1), and serum endotoxin. Participants will return a stool sample collected on day 13 of the intervention period at home. Participants will ingest a sugar solution containing 75 g glucose, which we and others have routinely shown to provoke oxidative stress responses including lipid peroxidation. This will be co-ingested with 1 g sucralose, 1 g erythritol, 5 g lactulose, and 1 g mannitol for assessment of gut permeability. Then, at 30 min intervals during the 3 h postprandial period, we will assess blood markers. During each study visit, participants will have access to drinking water

and use of the restroom as needed. Urine will be collected during the 3 h postprandial period in the laboratory, and participants will be instructed on urine collection for when they return home following their laboratory visit. Participants will return to the study center the following day to drop off their 24-h urine collection tubes. To ensure that the order by which each participant completes each trial is randomized, a random sequence generator (<http://www.random.org/sequences/>) will be used to determine the order by which each participant will undergo the two trials.

Sugar Probe Test. On the morning of testing at day 14, participants will arrive at the study center after abstaining from food and only consuming water for 10-12 hours. A sugar probe test will be conducted as described.⁵⁶ Upon arrival, participants will be asked to empty their urinary bladder. Subsequently, they will then be asked to ingest a drink containing 1 g sucralose, 1 g erythritol, 1 g mannitol, and 5 g lactulose dissolved in 75 g glucose (240 mL). Within 2-hours after ingesting the sugar test beverage, participants will be asked to consume an additional 500 mL of water. Additionally, participants will be provided with standardized sucrose, erythritol, mannitol, and lactulose-free meals (e.g. bagel, peanut butter, scrambled eggs) during the 24-h period. All foods consumed during the 24-hour period will be free of artificial sweeteners. Urine will be collected from 0-5 and 6-24 hours in sterile containers. For each urinary collection period, participants will be provided 2-L urine collection bottles and an insulated reusable bag with ice packs to store collected urine until they return their samples the next day.

Sampling Handling. Once at baseline (d 0), once at d 7, and at each time point of the postprandial trial a blood sample (14 mL, 4 mL, and 20 mL x 7 time points = 140 mL, respectively) will be collected into evacuated blood collection tubes. Collecting a total of 158 mL or 0.67 cups once at baseline, once at d 7, and during the postprandial trial is necessary to ensure adequate amount of plasma and serum for each time point to accurately analyze levels of glucose, insulin, endotoxin, gut hormones, and TLR4/NF κ B signaling genes. During blood collection, participants may feel an initial pain when inserting the needle, bruising around the insertion area, lightheadedness, or fainting, which are common when donating blood. However, we do not foresee any additional significant risks for collecting this amount of blood over 3 hours, other than the risks stated previously. Breath samples will be collected in a clean breath collection bag supplied with a sterilized disposable mouth piece. Participants need to breathe into the bag at their normal breathing speed. Generally, three to five regular breaths will be sufficient to fill the breath bag, and there is no risk associated with this procedure.

Throughout the span of the study (~8-12 weeks in duration depending on participant/investigator availability) which consists of four weeks total of controlled feeding, a blood collection at day 0, 7 and 14 and then repeated following a \geq 2 week washout period, and 1 screening day, we will be collecting a total of ~324 mL or ~1.37 cups) of blood. Urine will be collected in provided containers (VWR) containing 10% thymol to inhibit bacterial growth. We will then have the participants return their urine samples to the study center or coordinate with study personnel to meet at a public and mutual location to return their samples within 24-h after collection. Feces will be collected using a commercial commode specimen collection system (Fisher Scientific). Briefly, the collection kit consists of the necessary materials (e.g. gloves, waste bag) for participants to easily and hygienically collect their stool without contaminating the sample or themselves. Volumes of urine will be recorded and fecal mass and observations will be recorded based on the Bristol Stool Chart.⁶⁷

During each blood collection, plasma will be obtained by centrifugation and then transferred to cryogenic storage tubes. Serum samples will be obtained by allowing the blood to clot, followed by centrifugation and transfer to cryogenic storage tubes. Tubes will be stored at -80° C until analysis can be completed. Analyses will include plasma glucose, insulin, triglyceride, HDL cholesterol, TLR4, CD14, MD2, MyD88, p65, IL-1, IL-6, IL-8, TNF- α , MCP-1, GLP-1, GIP, and serum endotoxin. Urine will be stored at -80°C until analysis can be completed. Analysis from urine will include sucralose, erythritol, lactulose, and mannitol. Fecal samples will be stored at -80°C until analysis can be completed. Feces analysis will include microbiota composition, calprotectin, myeloperoxidase (MPO), and fecal short chain fatty acids (butyrate, acetate, propionate). Remaining plasma, serum, urine, and fecal samples not used for these analyses will be archived for 5 years at -80 C in the event we decide to measure additional inflammatory, antioxidant, or microbiota related markers. Appropriate notation has been made in the informed consent to alert participants that we will be archiving specimens and that they have the right to refuse our use of these specimens for future analyses. Lastly, approval from OSU IRB will be sought via a protocol amendment prior to the analysis of any additional biomarkers not specified herein.

Privacy/Confidentiality. For all data and records that are a part of this study, a number (i.e. code) will be assigned to each participant and will only be available to research personnel. Any records containing the names of participants will be stored in a locked filing cabinet or on a password protected computer in the PI's laboratory or office. Research personnel under the supervision of the PI and the PI himself will be the only individuals that have access to this information. The names of participants will not be used for publication in any form. The records will be maintained until the data are published, up to a maximum of five years. All archived samples will be coded, but the key linking the code to each participant's identifiable information will have been destroyed. In addition, participants will be instructed that their participation in this study is voluntary and that they may withdraw at any time without prejudice. Data (biochemical values) obtained from this study will be stored on a computer in the PI's laboratory. In addition, a backup of digital data will be stored on the PI's computer in his office. Both computers are password protected and both doors are locked when work areas are not in use.

E. Internal Validity

For all data and records that are a part of this study, a number (i.e. code) will be assigned to each participant. This will minimize measurement bias when performing analysis on dietary records, and biochemical markers because all samples/records will be coded. The codes will only be broken once data analysis has been completed and verified by the PI.

F. Medical Safety Plan

All aspects of the clinical study will be conducted in [name] clinical lab located in [name]. Participants will be fasted for 10-12 hours prior to each study visit. We recognize that certain risks associated with fasting include: hypoglycemia, weakness, and fainting. This duration of fasting is consistent with guidelines set forth by the American Diabetes Association to minimize risk to the individual⁶² when determining fasting blood glucose concentrations.

Risks related to hypoglycemia are anticipated to be low due to many participants' already elevated fasting blood glucose (study entry criteria = 100-126 mg/dL). They will also be ingesting a glucose beverage containing 75 g of glucose immediately following the fasting period. Throughout each visit to the study center, participants will be closely monitored by [name], [name] and [name] (Postdoctoral Fellow and Doctoral Students), all of them are members of the research team. They will monitor the safety and well-being of participants for any signs and symptoms of hypoglycemia including: confusion, dizziness, irritability, weakness, headaches, and fainting. [name] is certified by the Red Cross in CPR and basic first aid. Additionally, [name] (PI; [name]) has an academic office in close proximity to the study center and has significant experience coordinating clinical research studies involving overnight fasting, and other dietary- and carbohydrate-challenges, thereby supporting the competency of our research team in managing potential adverse events relating to fasting glucose and glycemic responses.

Consistent with our prior studies of similar design, and to ensure participant safety, all procedures throughout each study visit will occur while positioned on a hospital bed in the prone position. In the event that a participant was to become weak, dizzy, or faint, they would already be ideally positioned to minimize risks associated with these symptoms. In the event that hypoglycemia-related symptoms occur, the study would be terminated to allow the participant to recover. We are prepared to provide pre-packaged beverages and snacks containing simple carbohydrates (e.g. Gatorade, fruit juice, apple sauce, crackers) that will allow for rapid restoration of blood glucose. These food items will be stored in a refrigerator, located in close proximity ([name]), that is dedicated for foods used in research studies. Participant status (e.g. attentiveness, skin color) will be monitored in our clinical laboratory to ensure recovery. The clinical area where participants undergo blood draws is also equipped with first-aid measures (e.g. smelling salt) and all study team members are trained to assist with basic first-aid application if needed.

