Our “whole food” approach that matches nutrient profiles between study arms will maximize translation of the benefits of full-fat milk that are driven, at least in part, by MFGM. The dose of MFGM at 10-times that in whole milk also reflects that consumers obtain MFGM from dairy foods other than milk. As major outcomes, we expect to demonstrate novel evidence that MFGM-enriched dairy milk decreases metabolic endotoxemia and improves glucose tolerance in MetS adults by increasing gut barrier integrity in association with alleviating gut dysbiosis and inflammation. This will be of *significance* because MetS affects ~35% of Americans,⁴⁸ and is driven by inflammation attributed to poor gut health that leads to excess absorption of bacterial endotoxins. Thus, dietary management of endotoxemia with dairy milk could significantly impact the incidence of MetS while helping to explain outcomes of observational studies suggesting benefits of full-fat milk for weight management.⁴⁹ Ultimately, this study could help to debunk long-standing dogma that targets full-fat

dairy for energy reduction⁵⁰ and support evidenced-based recommendations as part of forthcoming *Dietary Guidelines for Americans*.

III. Procedures

A. Study Design

We will enroll male and female MetS adults (n = 24; 18-65 y) to complete a *2-arm, double-blind, randomized controlled, crossover trial*. They will be randomized in 4-unit blocks to receive, for 14 d, a controlled diet with dairy milk (3.5% fat; 3 servings/d) enriched with MFGM-derived phospholipid or a matched dairy milk that instead contains coconut and palm oil (control). We will provide *all* foods during each study period to ensure weight maintenance and to increase homogeneity of gut and host responses (see *Dietary Control*).

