
Power Calculation and Data Analysis. [name] (biostatistician; see *Letter of Support*) performed a power analysis using endotoxin (d 14) as the primary outcome. No human studies have examined MFGM on endotoxemia. Thus, we used our data from MetS and healthy persons in which fasting endotoxin was measured 5-times at 2-wk intervals. On average, endotoxin was >2-times higher in MetS ($P<0.0001$), and did not differ ($P>0.4$) by time or gender. We then calculated the mean difference in endotoxin between healthy and MetS subjects (16.4 ± 7.8 vs 32.4 ± 4.4 EU/mL, CV =48% vs 15%). Power analysis indicated that only 8 subjects/group would be required to obtain 95% power ($\alpha = 0.05$) using the larger of the two CVs. For the proposed study in only MetS persons, we estimated that MFGM would result in a conservative improvement of 60% of the difference in endotoxin in the MFGM vs control phases: $((32.4-16.4) \times 0.6 = 9.6$ EU/mL); CV = 32% (SD = 10.4). Thus, we would have ~90% power ($\alpha = 0.05$) with 14 MetS persons completing both study arms. Our targeted enrollment of 24 MetS persons (12F/12M) is therefore expected to be powered strongly to examine MFGM on endotoxemia. This will also account for attrition (estimated at 10%) and provide sufficient power to consider gender x treatment interactions.

Most data will be analyzed by linear mixed effects models with random effect for subjects (to account for repeated measures) and fixed effects for treatment, gender, time period, and their interactions. Multivariate regression will define correlations between variables with consideration of potential covariates. Significance for all analyses will be set at $P<0.05$.

C. Measurement/Instrumentation

Anthropometric Parameters and Blood Pressure. At screening, day 0, 7, and 14, participants will rest for 15 minutes prior to determining blood pressure using an automated cuff. BMI will be calculated from height determined from a wall-mounted stadiometer and weight from a calibrated scale. Waist circumference will be assessed at the level of the umbilicus using a nonflexible measuring tape.

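### The plan claims sufficient power for gender x treatment interactions, but its planning inputs give about 54% for an interaction as large as the whole assumed effect and about 18% for half of it

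*Combined protocol and SAP*

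**What the plan says.** All of this is in the Power Calculation and Data Analysis paragraphs of section III.B, unless noted.

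- The biostatistician "performed a power analysis using endotoxin (d 14) as the primary outcome". The assumed benefit is 60% of the gap between metabolic syndrome and healthy subjects (32.4 v 16.4 EU/mL), which is 9.6 EU/mL, with a CV of 32% (SD 10.4).
- From this, "we would have ~90% power ($\alpha = 0.05$) with 14 MetS persons completing both study arms".
- The sample size is then set: "Our targeted enrollment of 24 MetS persons (12F/12M) is therefore expected to be powered strongly to examine MFGM on endotoxemia". The next sentence adds: "This will also account for attrition (estimated at 10%) and provide sufficient power to consider gender x treatment interactions".
- The mixed model contains "fixed effects for treatment, gender, time period, and their interactions", and every analysis is tested at P<0.05.
- Section III.A describes a two-arm crossover in which participants are allocated in blocks of four. The Test trials paragraph of III.D adds that a random sequence generator sets each participant's order. Neither place mentions stratification by gender.

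The plan gives no gender x treatment effect size, no power figure for it and no calculation.

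**The concern.** In a crossover each person receives both milks, so the treatment effect is a within-person contrast and gains from that. Gender does not vary within a person. The gender x treatment interaction is therefore a comparison of two independent groups: the MFGM-minus-control differences in women against those in men. A sample that is ample for the first contrast can be far too small for the second, and the plan carries its assurance from one to the other without a calculation.

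The stake is interpretation. The interaction is a term in the stated model and is tested at P<0.05. A reader told that the test had sufficient power may well take a non-significant result as evidence that the effect is the same in women and men. With power near one half, the test would miss an interaction equal to the full assumed effect about 46% of the time.

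**Working it through.** **Inputs** (section III.B)

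- Treatment effect: (32.4 − 16.4) × 0.6 = 9.6 EU/mL.
- SD: 32% of 32.4 = 10.37, given as 10.4. The plan does not say whether this is a per-arm SD or the SD of the paired difference.
- Alpha 0.05. Sidedness is not stated; two-sided is assumed.
- Completers: 24 × 0.9 = 21.6, about 22, or 11 per gender.
- Interaction size: not given. The benchmarks used here are 100%, 75% and 50% of the assumed effect: 9.6, 7.2 and 4.8 EU/mL. An interaction of 9.6 means, for example, the full effect in one gender and none in the other.

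**Step 1: reproduce the plan's figure.** Paired t test, n = 14, SD of differences 10.4:

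- SE = 10.4/√14 = 2.78; noncentrality = 9.6/2.78 = 3.45; 13 df.
- Power = 89.1%, which matches about 90%.
- With 22 completers, SE = 10.4/√22 = 2.22 and power = 98.5%.

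A one-sided test gives 94.8%. Reading 10.4 as a per-arm SD with zero correlation gives 61.8%. The two-sided test with 10.4 as the paired-difference SD is the reading that fits, so it is used below.

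**Step 2: standard error of the interaction.** SE = SD × √(1/n_F + 1/n_M) = 10.4 × √(1/11 + 1/11) = 4.43. This is twice the 2.22 for the treatment effect in the same 22 people.

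**Step 3: power for the interaction.** Two-sided two-sample noncentral t on the within-person differences, SD 10.4:

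| Completers (F/M) | 9.6 EU/mL | 7.2 EU/mL | 4.8 EU/mL |
|---|---|---|---|
| 12/12 (no attrition) | 58.0% | 36.8% | 19.1% |
| 11/11 | 54.0% | 34.0% | 17.8% |
| 11/10 | 51.8% | 32.5% | 17.1% |

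Simulation at 11/11 agrees (54.2% and 17.9% for 9.6 and 4.8). Even a one-sided test gives only 67% and 27%.

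**Step 4: what the design can resolve at 11/11.**

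- 95% CI half-width: 2.086 × 4.43 = 9.25 EU/mL, almost the whole assumed treatment effect.
- Interaction detectable with 80% power: 13.06 EU/mL. This is 13.06/9.6 = 136% of the assumed effect and 13.06/16.0 = 82% of the whole gap between metabolic syndrome and healthy subjects.
- Completers needed for 80% power: 20 per gender for 9.6 EU/mL and 75 per gender for 4.8 EU/mL.

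**Step 5: sensitivity to the SD.** If the quoted SD s is per arm, the SD of the difference is s√(2(1 − ρ)), where ρ is the unstated within-person correlation. The value 4.4 is the SD that the plan reports for its earlier metabolic syndrome subjects.

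| Per-arm SD | ρ | SD of difference | Treatment effect, n = 14 | Interaction 9.6, 11/11 | Interaction 4.8, 11/11 |
|---|---|---|---|---|---|
| 10.4 | 0 | 14.71 | 62% | 31% | 11% |
| 10.4 | 0.5 | 10.40 | 89% | 54% | 18% |
| 10.4 | 0.75 | 7.35 | 99% | 83% | 31% |
| 4.4 | 0 | 6.22 | >99% | 93% | 41% |
| 4.4 | 0.5 | 4.40 | >99% | >99% | 68% |
| 4.4 | 0.75 | 3.11 | >99% | >99% | 93% |

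Only the second row returns the plan's figure of about 90%.

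**The case against.** The strongest reply is that 54% depends on two inputs the plan does not supply. It states no interaction size, so 9.6 and 4.8 EU/mL are benchmarks chosen here. It also does not say that 10.4 is the SD of a paired difference; as 32% of a mean level, it reads more naturally as a per-arm SD. Moreover, the trial enrols only people with metabolic syndrome, whose observed SD was 4.4. On that value an interaction of 9.6 EU/mL would be well powered, and with a high enough within-person correlation so would half of it.

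This stands as a caveat: both inputs are assumptions and must be stated as such. It does not rescue the claim. The plan chose 10.4, not 4.4, as its planning value, and 4.4 would give over 99% power with 14 completers instead of about 90%. The same conflict arises with 10.4 per arm and a correlation of 0.75. The benchmark of 9.6 is also generous, since smaller interactions do worse.

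Other points have some force. Power to consider an interaction is soft wording. Gender appears in no objective or hypothesis, and the primary comparison is untouched. These limit how serious the point is. The sentence is still an explicit power statement used to support the sample size. The plan's report that endotoxin did not differ by gender in the investigators' previous data concerns levels, not response to treatment. Finally, the absence of gender stratification is inferred from silence, and none of the power figures depends on it.

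**Conclusion.** The concern holds. On the planning inputs that reproduce the plan's figure of about 90%, power for the gender x treatment interaction with 22 completers is 54% at 9.6 EU/mL, 34% at 7.2 and 18% at 4.8; 80% is reached only near 13.1 EU/mL. Attrition does not explain the shortfall, because full completion gives 58% at most for 9.6. The result assumes that 10.4 is the SD of the within-person difference, a two-sided test at 0.05, equal numbers of women and men, and interaction sizes set as fractions of the assumed treatment effect. A much smaller true SD would raise the power, but the plan did not plan on one. The treatment comparison is unaffected; what is wrong is a stated property that the design does not have on its own inputs. It should be corrected.

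**What to change.** 1. In section III.B, delete the statement that the sample gives sufficient power for gender x treatment interactions.
2. State instead that the interaction is exploratory, that about 22 completers give about 54% power for a 9.6 EU/mL difference in effect between genders, and that 80% power is reached only near 13 EU/mL. State that 10.4 is taken as the SD of the within-person difference.
3. Report the treatment effect in each gender, and the interaction, with 95% confidence intervals. Do not conclude that there is no gender difference from P>0.05.
4. Take the primary treatment effect from the model without the gender x treatment term. With equal genders and effect coding the estimate is the same, so this mainly removes ambiguity about which coefficient is primary.
5. Optionally, run the blocks of four within gender (12 = 3 blocks of 4) so that sequence is balanced in each, and align the III.A and III.D descriptions of allocation. This does not repair the power.

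The cost is protocol wording and, if item 5 is taken up, a separate block list per gender. No extra participants are needed. The price is a less favourable power statement.

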Summary. This overview demonstrates that: 1) low-grade inflammation in MetS is attributed to endotoxemia in association with poor gut barrier integrity, 2) endotoxemia is causally-related to the initiation of obesity and insulin resistance³⁵ and circulating endotoxin is prognostic of progressive liver function deterioration,³⁶ 3) MFGM constituents provide antiinflammatory and prebiotic activity at the gut and attenuate endotoxemia, and 4) increased SCFAs from commensal bacteria of the gut not only improve gut integrity, but also promote intestinal incretin secretion to help manage glucose intolerance. Thus, our translational studies in MetS persons are expected to provide novel evidence that MFGM exhibits antiinflammatory activity to enhance glucose tolerance by attenuating endotoxemia. These findings would be of *significance* to public health because could they help to establish that dietary fat "quantity" is not necessarily detrimental to MetS risk, but rather fat "quality" potentiates host health due to enhanced gut barrier function. This would lead to evidence-based recommendations to help reverse course of dietary trends indicating that dairy consumption decreases in an age-dependent manner and that ~90% of Americans fail to meet the daily recommended intake of dairy.³

Anticipated Results

We expect the intervention to result in high compliance (>95%), consistent with our rigorous approach to provide all foods and test beverages.

In *Obj 1*, MFGM is *expected* to time-dependently decrease serum endotoxin (i.e. d 0 to d 14), and lower day 14 endotoxin compared with coconut and palm oil-enriched milk. MFGM will also attenuate meal challenge-induced increases in gut-derived endotoxemia. These benefits will correlate with improved gut barrier function as indicated by: 1) decreased urinary recovery of sugar probes (i.e. increased gut integrity), 2) increased fecal SCFA levels; these potentiate intestinal junction protein expression,²⁸ and 3) an alleviation of gut dysbiosis (e.g. microbial diversity, *Firmicutes:Bacteroidetes* ratio). Indeed, we expect reduced gut bacteria abundance. This is important because intestinal bacteria overgrowth provokes metabolic disease.^{37,38} Likewise, MFGM-mediated

prebiotic effects are anticipated to increase commensal bacteria (e.g. butyrate producers) and its anti-microbial activities are expected to reduce pathogenic populations (e.g. pyrogenic bacteria, decreased LPS synthesis).

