In *Obj 2*, we *expect* that MFGM will improve glucose tolerance based on decreased fasting glucose (d 14) and attenuated postprandial glycemic responses following the test meal challenge. This will be attributed to antiinflammatory activities of MFGM at the gut (i.e. decreased calprotectin and myeloperoxidase) and on host expression of TLR4/NF κ B genes (e.g. TLR4, IL-6). These antiinflammatory benefits are important because they potentiate intestinal GLP-1 and GIP secretion. These incretins improve insulin sensitivity and alleviate glucose intolerance by enhancing pancreatic β -cell function, and hence insulin secretion.³²⁻³⁴ Decreased TLR4/NF κ B signaling will also help to limit metabolic derangements that mediate glucose intolerance in MetS.¹

Pitfalls and Alternatives

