Recruitment. We acknowledge the challenge to recruit MetS adults for a nutrition study. Consistent with our studies,³⁹⁻⁴¹ we will consult the recruitment office of the OSU CCTS for assistance. They maintain a participant database (>126K registrants) and provide marketing support for study recruitment (e.g. social media, printed flyers, e-newsletters reaching ~100K faculty/staff and students at OSU). If difficulty is encountered to recruit MetS persons, we can modify our approach to focus on persons with prediabetes. Endotoxemia and Gut Integrity. We plan to consider endotoxin levels as a covariate in relation to other study endpoints. Also, while we are experienced in measuring endotoxin,^{15,16,39,42,43} we are mindful of the experiences of others where these measurements were problematic.⁴⁴ If necessary, we will use an alternative assay for LPS as we described,³⁹ and/or measure surrogate markers of endotoxin exposure (LPS binding protein, soluble CD14) as we described.^{42,43} There is the possibility that MFGM may reduce circulating endotoxin without affecting gut integrity. This would indicate that MFGM regulates endotoxemia likely by reducing populations of Gram-negative bacteria or functions of bacteria relating to LPS biosynthesis (to be tested in *Obj 1*) or alleviating transcellular absorption of excess LPS within chylomicrons. If MFGM does not alter taxonomic composition of the microbiota, metagenomic and metatranscriptomic analysis^{45,46} could be performed to define microbiota functionality. If MFGM does not improve glucose tolerance, we will assess triglyceridemia consistent with milk sphingolipid attenuating hepatic triglyceride in response to a high-fat diet.⁴⁷ In the event that gut inflammation is unaffected, we will consider untargeted metabolomics of archived fecal samples to identify metabolite patterns in response to MFGM. Lastly, our approach to evaluate postprandial responses considers “net” AUC to reflect metabolite concentrations that increase and/or decrease relative to baseline. If this approach lacks sufficient sensitivity to detect between-treatment differences, we will calculate incremental AUC scores to only consider those changes to rise above baseline values.

Significance of the Research and Potential Benefits

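### Day-14 endotoxin is the one named primary outcome, but glucose tolerance and further endotoxin tests are also main claims at an unadjusted P<0.05, with no rule linking them to it

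*Combined protocol and SAP*

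**What the plan says.** All places are in the combined protocol and SAP.

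- **Primary outcome.** Under Power Calculation and Data Analysis (section III.B), the biostatistician "performed a power analysis using endotoxin (d 14) as the primary outcome". No other outcome is called primary, and no other outcome has a calculated power figure.
- **Threshold.** The same section ends: "Significance for all analyses will be set at $P<0.05". No testing order, alpha split, adjustment, or secondary or exploratory label appears anywhere.
- **Two main claims.** Section I sets out two objectives, gut barrier function with endotoxemia, and glucose tolerance. Significance of the Research and Potential Benefits puts both effects together: "As major outcomes, we expect to demonstrate novel evidence that MFGM-enriched dairy milk decreases metabolic endotoxemia and improves glucose tolerance in MetS adults".
- **Several tests per claim.** Anticipated Results expects MFGM to "time-dependently decrease serum endotoxin (i.e. d 0 to d 14), and lower day 14 endotoxin compared with coconut and palm oil-enriched milk", and adds "MFGM will also attenuate meal challenge-induced increases in gut-derived endotoxemia". For Objective 2 it expects that "MFGM will improve glucose tolerance based on decreased fasting glucose (d 14) and attenuated postprandial glycemic responses following the test meal challenge".
- **A second attempt.** Pitfalls and Alternatives plans net AUC for postprandial responses and then says: "If this approach lacks sufficient sensitivity to detect between-treatment differences, we will calculate incremental AUC scores".
- **Marker panel.** Sampling Handling (section III.D) lists ten inflammatory signalling markers: TLR4, CD14, MD2, MyD88, p65, IL-1, IL-6, IL-8, TNF-α and MCP-1.

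**The concern.** Naming a primary outcome protects the conclusion drawn from that outcome. It does not protect other conclusions unless the plan says how they depend on it, and this plan does not. Followed as written, a trial with no difference in fasting day-14 endotoxin could still report that MFGM improves glucose tolerance, from one of several unranked tests at P<0.05. A positive postprandial endotoxin result could likewise stand in for a null fasting one.

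The objectives are not written as a pair that must succeed together: Pitfalls and Alternatives provides separately for glucose tolerance failing to improve. The same section's move from net to incremental AUC when the first shows no difference gives the postprandial tests a further, results-driven chance. The authors hope these outcomes will inform dietary guidance, so the standing of the second claim matters.

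**Working it through.** **1. The plan's own figure.** Difference 0.6 × (32.4 − 16.4) = 9.6 EU/mL; SD 10.4; 14 completers; α = 0.05. Standardised difference 9.6/10.4 = 0.923; noncentrality 0.923 × √14 = 3.45. A two-sided paired t test on 13 df has power 89.1%, which matches the stated ~90%. (The plan does not state sidedness; one-sided gives 94.8%. The match takes 10.4 as the SD of within-person differences.) So the plan in effect already spends a two-sided 0.05 on day-14 endotoxin.

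**2. Completers.** 24 × (1 − 0.10) = 21.6, taken as 21.

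**3. Tests counted.** Four between-milk tests: fasting day-14 endotoxin, postprandial endotoxin, fasting day-14 glucose, postprandial glucose. The day 0 to day 14 endotoxin change, the incremental AUC fallback and the gender interactions are not counted.

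**4. Independent tests.** The chance of at least one P<0.05 with no true effect is 1 − 0.95^k.

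- k = 2: 1 − 0.9025 = 9.75%
- k = 4: 1 − 0.8145 = 18.5%
- k = 10: 1 − 0.5987 = 40.1%
- Benefit direction only, k = 4: 1 − 0.975⁴ = 9.6%

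**5. Correlated tests.** The documents give no correlations, so a common value is assumed. Simulated paired t tests with 21 completers, no true effect, two-sided 0.05 (200,000 trials; 100,000 for the panel):

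| Reading | corr. 0 | corr. 0.5 | corr. 0.8 |
|---|---|---|---|
| Named primary alone | 5% | 5% | 5% |
| One test per claim (2 tests) | 9.7% | 9.1% | 7.9% |
| Any of four tests | 18.5% | 15.7% | 11.6% |
| Any of four, benefit direction (nominal 2.5%) | 9.7% | 7.8% | 5.8% |
| Primary, or both glucose tests in the same direction | 5.1% | 5.5% | 5.8% |
| Ten-marker panel, one time point | 39.9% | 29.6% | 18.0% |

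Large-sample normal statistics give 11.4% for four tests at correlation 0.8, so the four-test range is about 11–19%. Counting the day 0 to day 14 endotoxin comparison as a fifth test gives 22.6%, 18.8% and 13.1%.

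**The case against.** The strongest reply is that the plan does have a hierarchy: one primary outcome, with the sample size justified on it. That stands for the primary conclusion. A reader might infer that the plan has no hierarchy at all; the power section does not support that. What is missing is a rule below the primary.

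Second, the main claims are directional: MFGM lowers endotoxemia and improves glucose tolerance. A false result favouring control produces neither, so the relevant rate for a false claim of benefit is about 6–10%, not 11–19%. This also stands, although the proper comparison is then 2.5%.

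Third, the Objective 2 sentence joins fasting and postprandial glucose with the word and. If both must succeed, and postprandial endotoxin supports no claim of its own, the rate falls to about 5–6%. The reading is possible, but it rests on one conjunction in a passage about expected results, and the postprandial endotoxin expectation is written as a separate statement. The analysis section adopts no such rule.

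Fourth, Anticipated Results and Significance are narrative, and the signalling genes are offered as an explanation of the glucose result. It is therefore right not to count the panel as a headline error. But the only operative rule gives every analysis 0.05, so nothing in the plan separates narrative from confirmatory claims.

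Finally, which glucose measure to rank is a choice, and making it exploratory when endotoxin misses is a real loss for one of only two objectives. Both points are fair and belong in the fix.

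**Conclusion.** The point holds in limited form. The day-14 endotoxin test keeps its 5%. Across the two main claims the error is not controlled, and its size depends on a success rule that the plan does not state:

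- about 11–19% for any false P<0.05 among four tests, or about 6–10% for a false benefit against 2.5%;
- about 8–10% two-sided with one test per claim;
- about 5–6% under the strictest reading.

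The ten-marker panel carries about 18–40% at one time point, as mechanistic support only; this treats all ten listed markers as one family.

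A reader might infer a single figure of about 16% in place of a promised 5%. The documents support neither half. Sixteen percent needs four tests, an assumed correlation near 0.5, and both directions counted. The plan sets a threshold per analysis and never states a 5% rate across claims. All ranges assume no true effect on any endpoint and a common correlation between 0 and 0.8.

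**What to change.** In Power Calculation and Data Analysis:

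1. State that the confirmatory test is MFGM versus control on day-14 fasting (0 min) serum endotoxin, two-sided 0.05.
2. Pre-name one glucose-tolerance measure as key secondary, for example day-14 postprandial glucose net AUC, tested at two-sided 0.05 only if the primary is significant. The investigators should choose the measure before unblinding.
3. Fix the AUC definition in advance, and amend Pitfalls and Alternatives so that incremental AUC is a sensitivity analysis, not a second attempt.
4. Report the other endpoints and the gender interactions as exploratory, with 95% confidence intervals. Give Benjamini–Hochberg-adjusted P values for the gene panel.
5. Limit the P<0.05 statement to the two ranked tests, and align the major-outcomes sentence in the Significance section.

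The fixed sequence holds the error across the two ranked tests at or below 5%, with no change in sample size or primary power. The cost is that the glucose-tolerance result is exploratory if endotoxin is not significant. If that is unacceptable, splitting alpha at 0.025 each also holds 5%. On the plan's own inputs, endotoxin power would then be 80.8% with 14 completers or 95.7% with 21.
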